Complete Title of Protocol: Exercise Snacks and Glutamine to Improve Glucose Control in Adolescents with Type 1 Diabetes

NCT: NCT03199638

Date: April 24, 2015

RESEARCH PLAN

I. Specific Aims : To determine whether the sustained use of short bouts of exercise ('exercise snacks'), with or without the administration of the amino acid glutamine results in diminished glycemic variability and/or improved glucose control in adolescent with T1 diabetes.

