There were 3 groups 1) SIT: uninterrupted sitting (control); 2) LW: sitting + 3 min bouts of light-intensity walking at 3.2 km/h every 30 min; and 3) SRA: sitting + 3 min bouts of simple resistance activities (alternating half-squats, calf raises, brief gluteal contractions and knee raises) every 30 min (see below).

Simple Resistance Activities – SRA's

Over 22 h, both LW and SRA significantly reduced mean [interstitial] glucose, time in hyperglycemia and glycemic variability (quantified via the SD of mean glucose and mean amplitude of glycemic excursions) relative to uninterrupted sitting (Table). These simple interruptions to sitting significantly reduced the time in hyperglycemia, mean glucose and glycemic variability in adults with T2D. **This approach has not been studied yet in adolescents with type 1 diabetes.**

Table (A) Participant Characteristics and (B) Effects of the Three Trial Conditions on Glycemic Control

(A) Participant characteristics		(B) Effects of the three trial conditions on measures of glycemic control over 22 h			
Characteristic	N or mean (95% CI)	Measure of glycemic control	SIT (control)	LW	SRA
Number of study participants	14 M 10 F	Time in hyperglycemia (%)	60.3 (49.2, 71.3)	37.5 (26.5, 48.6)**	26.5 (15.5, 37.6)**
Age (yr)	62.3 (64.8, 59.8)	Time in hyperglycemia (hr)	13.3 (10.8, 15.7)	8.3 (5.8, 10.7)**	5.8 (3.4, 8.3)**
BMI (kg/m ²)	33 (34.4, 31.7)	Mean interstitial glucose (mg/dl)	11 (10.2, 11.8)	9.4 (8.5, 10.2)**	8.6 (7.8, 9.4)**
HbA1c (%)	7.2 (7.5, 7)	SD of mean interstitial glucose	2.2 (2, 2.5)	1.9 (1.7, 2.2)**	1.7 (1.5, 2)**
Note: All participants were Metformin/diet controlled individuals with type 2 diabetes.		MAGE (mg/dl)	104.94 (92.11, 117.78)	85.5 (72.66, 98.34)**	76.18 (63.35, 89.02)**
SD=standard deviation; MAGE=mean amplitude of glycemic excursions. *difference from SIT ($P < 0.05$); **difference from SIT ($P < 0.001$); Analysed using multi-level mixed models, controlling for age and BMI. Data are mean (95% CI).					

IV. Research Design and Methods

In this protocol we will determine whether 'exercise snacks', alone or in combination with dietary glutamine supplementation over a period of 3 months improve glycemic control in adolescents with type 1 diabetes.

Inclusion/Exclusion Criteria:

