Twenty-four adolescents with T1D for at least 12 months, between 13-19 yr-old will be recruited after informed written consent from their parents and the youngsters themselves. We will strive to recruit patients with comparable phenotype in both groups. They will be of normal weight (BMI between 10th and <85th percentile) and will be in puberty (at least Tanner stage III breast or genitalia) with a HbA1c between 7.5 and 9%. Subjects will be on either multiple daily injections (MDI) or insulin pump therapy. They will be recruited among the ~1,000 patients with T1D followed at Nemours Children's Clinic Jacksonville. We will exclude subjects with biopsy proven celiac disease, cystic fibrosis, chronic steroid therapy, mental retardation, microalbuminuria or evidence of other diabetic complications. Subjects involved in an active exercise program or in an organized sport team will be excluded. Studies will be conducted at least 2 weeks after resolution of any intercurrent infection.

Procedures: All subjects will have a full physical exam including Tanner staging as well as waist circumference measurement. A HbA1c, will be obtained as well as fasting triglycerides. A continuous glucose monitor (CGM iPro®, Medtronic Minimed, or a DexCom ^4) will be worn blindly for 6 days and data downloaded. Subjects will then be randomized to 2 study groups of 12 patients each:

(A) an 'exercise group', in which subjects will perform daily 'exercise snacks' within 30 min before breakfast, lunch, and/or dinner or bedtime snack, along with a placebo drink;

(B) an 'exercise + glutamine group', in which subjects will receive a glutamine drink (0.25 g/kg per dose) before meals TID, and perform 'exercise snacks' before each meal.

[figure not shown]
Allocation to the exercise only or the exercise + glutamine group will be stratified according to HbA1c range (eg, 7.5-7.9%; 8.0-8.4%; 8.5-9.0%), so as to ensure the comparability of groups.

The placebo and glutamine drink will be prepared at home using measuring spoons of glutamine or placebo powder to be mixed in a calorie-free, flavored soft drink tailored to the child's individual taste. Patients, families and investigators will be blinded as to the contents of the supplement.

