-Calculations - An insulin sensitivity score (ISS) will be calculated as previously described using the SEARCH ISS model: $\log_e IS = 4.64725 - 0.02032(\text{waist, cm}) - 0.09779(\text{HbA1c, \%}) - 0.00235(\text{TG, mg/dl})$ ($R^2=0.74$ in the initial SEARCH model) [34-35]. This has been validated using the hyperinsulinemic euglycemic clamp, considered the gold standard for insulin sensitivity measures [34,35]. CGM data will be downloaded and used to calculate % blood glucose (BG) at, below or above target and the mean amplitude of glycemic excursions using a SAS program (MAGE) as previously described [17,21,22].

-Statistical Analysis and Statistical Power.

To determine whether short bouts of exercise and/or glutamine improve glycemic variability and diabetes control, we will compare the following parameters between baseline and 3 months:

- a) Changes in HbA1C
- b) Changes in MAGE
- c) Changes in % BG at target (70-180), below target (<70), above target (>180)
- d) Changes in ISS
- e) Changes in total insulin dosing (units/kg/day)

A mixed effects models and/or generalized estimating equations (GEE), which ever appropriate will be used within and between subjects and groups comparisons. Model assumptions will be checked by analyses. Significance will be established at $p<0.05$.

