-Sample Size Justification: A sample size of 24 patients is planned assuming no more than 10% attrition rate. The main judgment criterion will be the mean amplitude of glycemic excursion (MAGE, measured using CGM). In the Australian study by Dunstan et al. [36]—described above in the Preliminary results section of this application—performed in adults with type 2 diabetes, MAGE was 104.9 ± 12.8 mg/dl (mean \pm SD) in the sedentary group of patients with type 2 diabetes, vs. 76.2 ± 12.8 mg/dl—i.e., a drop by 28.7—in the group performing short bouts of resistance exercise. To the best of our knowledge, there is no earlier study of such type of exercise in adolescents with T1D published in literature. Assuming ‘exercise snacks’ will decrease MAGE to the same extent in our population of children with T1D as in adults with T2D, such reduction will amount to an effect size of $\delta/\sigma=28.7/12.8 \approx 2.24$, where δ is the expected change in MAGE ($104.9-76.2=28.7$), and σ^2 the estimated variance of MAGE ($\sigma=12.8$, calculated based on [name] et al’s data). Using equations for unpaired studies, the number (n) of subjects per group needed to detect such difference with an α risk <0.05 , and a statistical power($1-\beta$) of 80% can be estimated as: $n= 2 \times (Z_\alpha + Z_\beta)^2 / (\delta^2/\sigma^2)$ [37], where $Z_\alpha=1.96$, and $Z_\beta=0.84$, therefore $n=2 \times (1.96 + 0.84)^2 / (2.24)^2 = 2 \times 7.84/5.02=3.1$. The enrolment of 12 patients per group therefore should be amply sufficient to test our hypothesis, even if we take into account a putative 25% attrition rate.

- Future Directions: These simple and short resistance activities as it was shown in previous studies [16, 36] have significantly reduced the time in hyperglycemia, mean glucose and glycemic variability in adults with T2D. With the ubiquity of sedentary behaviors and the low adherence to structured exercise, this approach has the potential to be beneficial and practical. This interesting approach has not been studied yet with combination of glutamine in patients with type 1 diabetes.

V. Facilities Required/Physical Location of Study

This study will be performed in outpatient settings and will recruit patients who are followed at the deivision of Endocrinology at the Nemours Children’s Healthy System in Jacksonville.

VI. References

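### The trial asks whether exercise snacks work, but both randomised arms exercise, and the plan does not say which MAGE contrast decides

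*Combined protocol and SAP*

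**What the plan says.** Section I (Specific Aims) asks whether sustained use of exercise snacks, with or without glutamine, "results in diminished glycemic variability and/or improved glucose control". The opening of section IV repeats the question, and the Statistical Analysis section carries it into the analysis: "To determine whether short bouts of exercise and/or glutamine improve glycemic variability and diabetes control, we will compare the following parameters". Values at 3 months are set against baseline for five items: HbA1c, MAGE, percentages of glucose readings in, below and above target, the insulin sensitivity score, and total insulin dose. Mixed models and/or GEE "will be used within and between subjects and groups comparisons", with significance at p<0.05.

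Section IV, Procedures, describes two groups of 12. One does exercise snacks with a placebo drink, the other exercise snacks with a glutamine drink. "Allocation to the exercise only or the exercise + glutamine group will be stratified according to HbA1c range". No arm, period or crossover without exercise is described, apart from the baseline measurement.

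The Sample Size Justification states: "The main judgment criterion will be the mean amplitude of glycemic excursion". It assumes that exercise snacks "will decrease MAGE to the same extent in our population of children with T1D as in adults with T2D", takes 28.7 mg/dl from a comparison of resistance bouts with uninterrupted sitting, and puts it into a formula for two unpaired groups. It concludes that 12 per group is ample, even with 25% attrition.

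**The concern.** The comparison of the two arms addresses glutamine added to exercise. It says nothing about exercise itself, because both arms receive it. That half of the aim can be judged only from change since baseline, within an arm or pooled.

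Such a change also carries everything else that happens over the 3 months. Procedures lists weekly contact, gift cards for weeks with at least 50% compliance, and diet recording. Insulin dose is recorded and is itself a change outcome, and nothing states that it is held fixed. Blinding covers only the drink.

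The plan names MAGE as the main criterion but leaves open whether change within either arm, the pooled change or the difference between arms decides. A non-specific fall in MAGE would meet the only stated significance rule and could be reported as an exercise benefit. The one comparison protected by randomisation and blinding is neither made decisive nor given a power basis.

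**Working it through.** **1. The plan's own figure.** Inputs from the Sample Size Justification: difference δ = 104.9 − 76.2 = 28.7 mg/dl, σ = 12.8, Z values 1.96 and 0.84.

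n = 2 × (1.96 + 0.84)² / (28.7/12.8)² = 2 × 7.84 / 5.02 = 3.1 per group.

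This reproduces. However, the 28.7 compares exercise with sitting, whereas the two groups here are exercise + placebo and exercise + glutamine. The formula has the shape of the randomised comparison and the effect of a different one. The documents give no glutamine effect on MAGE.

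**2. The SD.** The table in section III, item d, gives MAGE under sitting as 104.94 with limits 92.11 and 117.78, labelled a 95% CI, for 24 participants. The half-width is (117.78 − 92.11)/2 = 12.835, which matches the plan's SD of 12.8. Read as a simple CI, the SD is 12.835 × √24 / 2.069 = 30.4 (t quantile) or 12.835 × √24 / 1.96 = 32.1 (normal quantile). Both readings are carried below.

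**3. Uncontrolled change.** Suppose exercise has no effect and MAGE drifts down for other reasons. The SD of the change is SD × √(2(1 − ρ)), where ρ is the baseline-to-3-month correlation. At ρ = 0.5 it equals the SD. For 24 pooled at SD 12.8, the standard error is 12.8/√24 = 2.61, so a 10 mg/dl drift has noncentrality 10/2.61 = 3.83. Probabilities of p<0.05 (two-sided paired t-test, noncentral t) at ρ = 0.5, with the range over ρ = 0.3 to 0.7 in brackets:

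| Drift | SD | One arm, n = 12 | Pooled, n = 24 |
|---|---|---|---|
| 5 mg/dl | 12.8 | 0.24 (0.18-0.36) | 0.45 (0.34-0.66) |
| 10 mg/dl | 12.8 | 0.69 (0.55-0.89) | 0.96 (0.87-1.00) |
| 5 mg/dl | 30-32 | 0.08 (0.07-0.10) | 0.11-0.12 (0.10-0.17) |
| 10 mg/dl | 30-32 | 0.17-0.18 (0.13-0.27) | 0.31-0.34 (0.24-0.51) |

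Drift sizes and correlations are assumptions; the documents give neither.

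**4. Undefined contrast.** With no true change and no drift, testing MAGE in each arm and between arms at 0.05 gives at least one p<0.05 in 11.5% of 200,000 simulated trials. Counting only favourable results (a fall in either arm, or glutamine better), it is about 6.6%.

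**5. What the randomised comparison can detect.** The normal approximation at 12 per arm is 2.80 × 12.8 × √(2/12) = 14.6 mg/dl. Using the noncentral t, with 80% power and two-sided 0.05:

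| Setting | SD 12.8 | SD 30.4-32.1 |
|---|---|---|
| 12 per arm, unadjusted | 15.3 | 36.4-38.4 |
| 12 per arm, baseline-adjusted at ρ = 0.5, SD × √(1 − 0.25), 21 df | 13.3 | 31.6-33.3 |
| 9 per arm (12 × 0.75), unadjusted | 18.0 | 42.8-45.2 |

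If glutamine had half the assumed exercise effect (14.35 mg/dl, an assumption), power at 12 per arm, unadjusted, would be 75% at SD 12.8 and 18-20% at SD 30-32.

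**The case against.** The best defence is that baseline serves as the control. Patients in an exercise program or organised sport are excluded, and glucose monitoring precedes randomisation, so the change to 3 months is roughly a move from low activity to exercise. Monitoring is blinded, diet is also recorded at baseline, and weekly contact and rewards could be seen as part of the program under test. This makes the before-after estimate worth reporting. It does not supply a concurrent control or remove regression to the mean and changes in insulin dose.

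The numbers can also be challenged. The drift results depend on assumed inputs and, at the larger SD, a 5 mg/dl drift raises the error rate only modestly. The 11.5% includes unfavourable results, and the one-directional 6.6% is small. The SD of 30-32 treats as simple an interval that came from a mixed model adjusted for age and BMI. All of this is fair, so the case rests on the design and not on any one figure.

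Finally, Procedures words the timing and frequency of the exercise differently for the two arms, while its later description gives one common schedule. These passages must be reconciled, since the comparison isolates glutamine only if the exercise is the same in both arms.

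**Conclusion.** The concern holds and must be fixed. The design cannot attribute a fall in MAGE to exercise snacks, the plan does not name the contrast that decides, and the power statement sizes a comparison the randomised arms do not form. These conclusions follow from the text and need no assumption about drift, correlation or SD.

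The size of the risk does depend on those assumptions. Across the values examined, the chance that a non-specific fall of 5-10 mg/dl passes p<0.05 runs from 0.07 to nearly 1.00. Unadjusted, with 12 per arm, the glutamine comparison has 80% power for about 15 mg/dl if the SD is 12.8. If it is 30-32, the detectable 36-38 mg/dl exceeds the whole 28.7 mg/dl assumed for exercise.

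**What to change.** 1. Name one confirmatory test: the difference between exercise + glutamine and exercise + placebo in 3-month MAGE, adjusted for baseline MAGE, two-sided 0.05. An arm-by-time contrast from the planned mixed model would also serve if specified in advance.
2. Reword the aim and the planned conclusion so that the randomised claim concerns glutamine added to exercise snacks.
3. Report within-arm and pooled changes as uncontrolled estimates with 95% CIs, without an efficacy claim for exercise based on p<0.05.
4. State in the Statistical Analysis section that the other measures are supportive, in line with the Sample Size Justification.
5. Replace the power statement with the detectable glutamine difference at 12 and at 9 per arm, shown for SD 12.8 and for SD 30-32.

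This changes wording in the aims, analysis and sample-size sections and needs no new arm or patients. The price is the causal exercise claim and a less favourable power statement. At the larger SD the trial may have to be described as an estimation or pilot study for glutamine. Keeping exercise as a confirmatory question would instead require a concurrent comparator without exercise snacks.

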a). Pilot studies on the effect of glutamine and exercise in adolescents with T1D [17]. Maura, et al, Diabetes Care 2011.

[figure not shown]
Post-exercise hypoglycemia is a common problem in youth with T1D. Approximately 20% of endogenous glucose production comes from gluconeogenesis via amino acid (AA) precursors, particularly GLN and AA depletion occurs in insulin-induced hypoglycemia. As GLN is a major contributor to gluconeogenesis, we studied the effects of GLN on glucose concentrations during afternoon exercise as well as overnight post exercise. We studied ten adolescents with uncomplicated T1D (mean age 15 ± 1 yr-old, 5M, 5F) who had been diabetic for 6.2 ± 3.3 years and wore insulin pumps, with a mean HbA1c of $6.9\pm0.9\%$, and a normal BMI (between the 10th and 85th percentiles). They were on no chronic medications.

Subjects were studied twice in the Clinical Research Center CRC during 1-h exercise session starting at 3PM. Mean blood glucose was in the mid 100 mg/dL range prior to exercise. Sessions consisted of 4, 15-min treadmill exercise (heart rate 140 bpm) with 5-min rest breaks interspersed. Blood glucose was continuously monitored during exercise and overnight. Basal insulin rates were continued during the study. Subjects were randomized to receive a drink containing either glutamine (before exercise and at bedtime (0.5 g/kg per dose), or a calorie- and nitrogen-free placebo. Studies were repeated within 3 weeks, and in randomized order. Plasma GLN concentrations measured 16 h post exercise the following morning were higher during the GLN study day than after placebo (316 vs. 200 μ mol/L, $p<0.001$).

However, regardless of the dietary supplement received prior to exercise, plasma GLN concentrations measured in the postabsorptive state the following day, were below normal as compared to healthy, age-matched controls measured at rest ($p<0.001$) [33]. In earlier studies performed under resting conditions and using the same assay, we consistently observed that adolescents with T1D had plasma GLN concentrations in the normal range at rest as normal age-matched controls (484 ± 25 vs. 513 ± 29 μ mol/L, NS) [33]. This suggests that intense exercise likely depletes plasma GLN in adolescents with T1D, as it does in healthy adults. Blood

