glucose was similar at baseline on both study days (143 ± 31 and 162 ± 54 mg/dL on the GLN and placebo study day, respectively; $p=0.44$), and blood glucose dropped comparably ($52 \pm 15\%$ vs. $52 \pm 9\%$ on the GLN and placebo study day, respectively; $p=0.84$) during exercise on both days. Yet overnight, post-exercise low blood glucose levels (defined as either <70 mg/dL or <60 mg/dL) were significantly more frequent ($P=0.03$, and 0.05 , respectively) after GLN than after placebo. The cumulative probability of overnight hypoglycemia was increased on the GLN day (80%) compared with placebo (60%, $p=0.02$, Fig 4). We concluded that GLN supplementation increases the incidence of post exercise nighttime hypoglycemia. [17]. Taken in aggregate, our preliminary studies suggest that, in adolescents with T1D performing heavy exercise, plasma GLN is low after exercise; and GLN supplementation increases the likelihood of hypoglycemia after exercise. As the patients studied presumably had no residual endogenous insulin secretion, our findings suggest that GLN may enhance glucose uptake and/or increase insulin sensitivity. These data, in addition to the data reviewed from other studies suggest that GLN supplementation may affect insulin sensitivity either at the peripheral or hepatic level in T1D. If proven true, these results could have important implications to improve glycemic control in T1D.

Fig.4 Time to post-exercise, nocturnal hypoglycemia (defined as first drop below 70mg/dL) in adolescents with T1DM after oral ingestion o glutamine or placebo [17]

b). Glucose-lowering Effects of Glutamine in Adolescents with Type I Diabetes [18] Torres, et, al (manuscript to be submitted for publication)

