Thirteen pubertal adolescents (15.96 ± 1.6 years [SD], 8M; 5F; BMI $69^{\text{th}} \pm 16$ centiles 6, HbA1C $8.2 \pm 0.5\%$, T1D: 7.5 ± 4 yrs) on insulin pumps were randomized to receive a drink with GLN or placebo pre-exercise, bedtime and early morning (0.25 g/kg/dose) in a double-blind crossover design over 4 weeks. Exercise session (3pm) consisted of four 15-min treadmill/5-min rest cycles. Blood glucose (BG) was monitored during exercise and overnight. The following morning, a 5-hr primed, continuous infusion of D-[6, 6- $^2\text{H}_2$] glucose was administered, during a 2-dose hyperinsulinemic, euglycemic clamp (low dose: $8 \text{ mU/m}^2/\text{min}$; high dose: $80 \text{ mU/m}^2/\text{min}$) in the post absorptive state. BG levels dropped comparably during exercise on both days. However, the total number of nocturnal hypoglycemic events (17 vs. 7, $p=0.045$) and the cumulative probability of overnight hypoglycemia (50% vs. 33%, ($p=0.02$) were higher on the glutamine day than on the placebo day. During clamp, glucose infusion rate did not differ between days ($7.7 \pm 1 \text{ mg/kg/min}$ vs. $7.0 \pm 1 \text{ mg/kg/min}$; glutamine vs. placebo; $p=0.4$). A correlation was noted between nocturnal hypoglycemic events and S_I on the glutamine day.

Our findings confirm our previous observations that glutamine has glucose-lowering effects in adolescents with type 1 diabetes after exercise no consistent change in insulin sensitivity was observed. Although a correlation was noted between nocturnal hypoglycemic events and insulin sensitivity on the glutamine day. The mechanisms mediating the effect of glutamine remain to be elucidated.

C). 'Exercise snacks' before meals to improve glycemic control in individuals with insulin resistance [16]. Francois, et al, Diabetologia, 2014

[figure not shown]

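### Both in-house pilots found more overnight hypoglycaemia on glutamine, but no overnight analysis is planned; pooling all CGM readings would shrink a mainly nocturnal difference (threefold only for an 8-hour night with no daytime effect)

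*Combined protocol and SAP*

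**What the plan says.** Section III.a (first glutamine pilot, ten adolescents, crossover) reports that overnight lows were more frequent after glutamine at both cut-offs examined, below 70 and below 60 mg/dL. It adds: "The cumulative probability of overnight hypoglycemia was increased on the GLN day (80%) compared with placebo" (60%). The investigators state: "We concluded that GLN supplementation increases the incidence of post exercise nighttime hypoglycemia".

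Section III.b (second pilot, thirteen adolescents, crossover) reports that "the total number of nocturnal hypoglycemic events (17 vs. 7" was higher on glutamine, as was the cumulative overnight probability (50% vs 33%). It describes this as confirming the earlier result.

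Section IV, Procedures, gives glutamine or placebo alongside exercise snacks, 12 patients per arm. Of the baseline CGM it says that it "will be worn blindly for 6 days and data downloaded". CGM is placed again for 6 days at 1 month, and the baseline studies, CGM included, are repeated at 3 months.

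Section IV, Statistical Analysis, lists five parameters to compare between baseline and 3 months. The only one that touches hypoglycaemia is (c): "Changes in % BG at target (70-180), below target (<70), above target (>180". It gives no overnight window, event count, cut-off below 60 or day/night split, and it does not name the 1-month CGM. The Calculations paragraph adds no window and refers to cited methods.

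**The concern.** The investigators' own data point to one specific harm of the supplement under test: more low glucose at night after exercise. The trial gives that supplement daily for 3 months and will record nights on CGM, but the analysis list contains nothing aimed at the night. Read naturally, parameter (c) averages overnight readings with daytime ones. If glutamine acts mainly at night, the average understates the difference between arms, and the trial could report no increase in time below target while the harm seen in both pilots is present.

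The efficacy results also become harder to interpret. Extra overnight lows can widen glucose excursions and so raise MAGE, the main criterion. They can also contribute to a lower HbA1c that would be read as benefit. An overnight analysis added after unblinding would be post hoc.

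**Working it through.** **The plan's own figure.** The only design calculation is for MAGE: n = 2 × (1.96 + 0.84)² / (28.7/12.8)² = 2 × 7.84 / 5.02 = 3.1 per group. It reproduces, but it says nothing about hypoglycaemia. The documents give no power, SD or expected level for % below 70.

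**Absolute dilution.** Let h be the length of the night in hours, w = h/24, and f the daytime glutamine effect as a fraction of the night effect. All-day % below 70 is the time-weighted mean of night and day, so

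night difference / all-day difference = 1 / [w + (1 − w)f].

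The documents give neither h nor f; both are assumptions.

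- No daytime effect (f = 0): the ratio is 24/h, which is 4.0 at 6 h, 3.0 at 8 h, 2.4 at 10 h and 2.0 at 12 h.
- 8-hour night (w = 1/3), f = 0.25: 1 / (1/3 + 1/6) = 2.0.
- 8-hour night, f = 0.5: 1 / (1/3 + 1/3) = 1.5.
- 8-hour night, f = 1: 1.0, so nothing is lost.

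**Why this does not convert to a sample-size factor.** Pooling changes the SD as well as the mean. Let k be the day/night SD ratio and r the day-night correlation. The sample-size factor is then [w² + (1 − w)²k² + 2w(1 − w)rk] / [w + (1 − w)f]². For an 8-hour night:

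| Daytime effect f | SD ratio k | Correlation r | Factor |
|---|---|---|---|
| 0 | 1 | 0 to 0.5 | 5.0 to 7.0 |
| 0 | 0.5 | 0 to 1 | 2.0 to 4.0 |
| 0 | 1.5 | 0 to 1 | 10 to 16 |
| 0.25 | 1 | 0 to 0.5 | 2.2 to 3.1 |
| 0.5 | 1 | 0 to 0.5 | 1.25 to 1.75 |
| 1 | 1 | 0 to 0.5 | 0.56 to 0.78 |

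In the last row the pooled measure is the more efficient one. With k, r and f all unknown, no single factor is defensible.

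**What an overnight measure could deliver.** A one-night yes/no comparison at 12 per arm would be weak. Treating the pilot probabilities as independent-group proportions (two-sided 0.05), power is about 18% for 80% vs 60% and 13% for 50% vs 33%. For 80% power about 82 and 131 per group would be needed. Counts over several nights carry more: 12 patients × 6 nights = 72 patient-nights per arm per visit if every night is usable, against 13 per condition in the second pilot. Nights within a patient are correlated, so the gain is less than that ratio suggests.

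**The case against.** Several points on the other side have force.

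- **The pilots do not show that the effect is confined to the night.** For the first, "Blood glucose was continuously monitored during exercise and overnight"; the second did the same. Other daytime hours were never compared. A reader might infer that a threefold loss is established; the documents do not support that.
- **The trial is not the pilot.** The pilots used one afternoon treadmill session with a bedtime dose, in pump users. The trial uses 6-minute bouts and pre-meal dosing, admits patients on injections, and follows insulin dose over 3 months. A daytime effect is plausible and would reduce the dilution.
- **Pooling is inferred.** Parameter (c) states no window, and the CGM methods are cited to earlier work that includes the first glutamine pilot. All readings is the natural interpretation, but the cited method cannot be checked here. An unstated window is still a gap that needs closing.
- **A reader might infer a fixed multiple of the sample size, or scale time below 70 by 17/7.** The first needs SDs that the documents lack. The second applies a ratio of event counts to a percentage of time.
- **A reader might infer that MAGE cannot be interpreted at all.** That goes too far: % below, at and above target are reported beside it, so more lows would not be wholly invisible.
- **Extra outcomes add comparisons, and precision at 12 per arm is limited.** This is true and governs how the results should be worded.

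None of this supplies the missing overnight analysis. It limits how large the loss can be said to be.

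**Conclusion.** The omission is real. Two in-house studies report more overnight hypoglycaemia on glutamine, and the plan pre-specifies no overnight window, event count or cut-off below 60, although the CGM it schedules would hold the data. On its natural reading, parameter (c) is a weaker test of that harm if the effect is mainly nocturnal. The absolute difference then shrinks by up to 24/h: threefold for an 8-hour night with no daytime effect, and 2.0 to 1.0 for a daytime effect of 25% to 100% of the night effect. Those figures rest on an assumed night length and an unknown daytime effect, and no sample-size consequence can be attached to them. This is a cheap improvement to the analysis plan, not a flaw that invalidates the design.

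**What to change.** Keep all-day % below 70, say explicitly that it uses all readings, and add to parameter (c), from the CGM already scheduled:

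- overnight % below 70 and below 60 mg/dL (the first pilot's two cut-offs), in a clock window fixed before unblinding;
- overnight hypoglycaemic events per night, under an event definition written in advance.

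Compare arms at 1 and 3 months, adjusting for the baseline value, with 95% confidence intervals. For events, use a count model with nights worn as the offset. Allow for repeated nights and visits within a patient by GEE or a mixed model, both of which the plan already names. Label this a pre-specified safety comparison and report it beside all-day % below 70 and MAGE, so that daytime lows are not pushed aside.

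The cost is some protocol wording and additions to the CGM program, with no new data, visit or procedure. The downside is a few more comparisons with limited precision at 12 per arm. The text should therefore say that they are read by their confidence intervals and that a non-significant result is not evidence of safety.
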